### **3.2 Proposed Primary and Secondary Outcome Measures**

#### 3.2.1 Primary Outcomes

The primary outcome is any unplanned secondary procedure within 2 years of the initial joint replacement surgery. A Central Adjudication Committee will review each reported secondary procedure to determine that they are study events (i.e. unplanned) and they will confirm the type of the procedure and the reason for the procedure (**Table 1**).

Specific unplanned secondary procedures include:

1. Closed reduction of hip dislocation
2. Open reduction of hip dislocation
3. Open reduction of fracture
4. Soft tissue procedure
5. Insertion of antibiotic spacer
6. Full implant exchange
7. Partial implant exchange – stem only
8. Partial implant exchange - head only
9. Partial implant exchange - liner only
10. Partial implant exchange - head and liner
11. Partial implant exchange – acetabular component only
12. Partial implant exchange – acetabular component and head
13. Implant adjustment – re-orientation of the stem
14. Implant adjustment – re-orientation of the acetabulum component
15. Implant removal with no replacement
16. Excision heterotopic ossification
17. Supplementary fixation

Classification of the reason for secondary procedures is as follows:

1. Treat a peri-prosthetic fracture
2. Treat hip instability or dislocation
3. Treat infection – superficial
4. Treat infection – deep
5. Treat wound necrosis
6. Treat another wound healing problem

7. Remove heterotopic ossification
8. Manage abductor failure
9. Manage another soft tissue problem (i.e. pseudotumor)
10. Correct implant failure –loosening or subsidence
11. Correct implant failure - breakage
12. Treat implant wear
13. Treat osteolysis
14. Treat implant corrosion
15. Improve function
16. Relieve pain

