## **4. SUBJECT SELECTION AND RISK**

### **4.1 Inclusion and Exclusion Criteria**

#### 4.1.1 Inclusion Criteria

1. Adult men or women aged 50 years and older (with no upper age limit).
  2. Fracture of the femoral neck confirmed with either anteroposterior or lateral hip radiographs, computed tomography, or magnetic resonance imaging (MRI).
  3. Displaced fracture that is not, in the judgment of the attending surgeon, optimally managed by reduction and internal fixation.
  4. Operative treatment within 3 days (i.e. 72 hours) of the patient being medically cleared for surgery.
  5. Patient was ambulatory prior to fracture, though they may have used an aid such as a cane or a walker.
  6. Anticipated medical optimization for arthroplasty of the hip.
  7. Provision of informed consent by patient or proxy.
  8. Low energy fracture (defined as a fall from standing height).
  9. No other major trauma (defined as an Injury Severity Score <17\*).
  10. Assurance that surgeons with expertise in both total hip arthroplasty and hemi-arthroplasty are available to perform surgery. Note: Surgeons do not need to be experts in both techniques.
- \*The Injury Severity Score (ISS) is an anatomical scoring system that provides an overall score for patients with multiple injuries. Each injury is assigned an Abbreviated Injury Scale (AIS) score and is allocated to one of six body regions (Head, Face, Chest, Abdomen, Extremities (including Pelvis), and External). Only the highest AIS score in each body region is used. The 3 most severely injured body regions have their score squared and added together to produce the ISS score. More information can be found at: <http://www.trauma.org/archive/scores/iss.html>.

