## **7. STATISTICAL PLAN**

## 7.1 Sample Size Determination

The choice of sample size is based upon a comparison for the primary outcome (secondary procedures) of THA versus HA. All statistical hypotheses will be two-sided. Alpha levels of 0.05 for the primary and 0.01 for the secondary outcomes were chosen. Previous studies have reported secondary procedure rates in hip fracture patients treated with HA that have ranged from 4 to 10% at one year, with a weighted pooled risk of 5.3% (95% CI 3.2 to 8.9%) in a fixed effect meta-analysis, or 4.9% (95% CI 2.6 to 9.2%) using random effects. A pooled estimate from 5 randomized trials comparing THA with HA gave a relative risk of 1.67 (95% CI 0.86 to 3.24,  $p=0.13$ ) (**Table 3a**).

The sample size calculation reflects the proposed approach to the primary analysis, which will use the Cox proportional hazards model. The calculation is based on methods described by Collett (Collett, 1994). The goal is to calculate the required number of patients that will yield a sufficient number of outcome events (secondary procedures) in order to have adequate statistical power for a given size of treatment effect. This was done taking into account the anticipated secondary procedure rates in the HA group, postulated values of the relative risk increase associated with THA vs. HA, and the rates of mortality and loss to follow-up. Because some of these inputs are expected to change over the two year period of follow-up, the expected number of person-years of follow-up and the expected numbers of study events in each group were calculated, initially for the first year of follow-up; the calculation was then repeated for the second year of follow-up, after having estimated the number of patients in each group who would survive, be event-free, and available for continued follow-up between 12 and 24 months post-randomization.

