## 7.2 Statistical Methods

### 7.2.1 Primary Analyses

All outcome analyses will be performed by an intention to treat approach. To evaluate the effect of total hip arthroplasty versus hemi-arthroplasty on time to secondary procedures (the primary outcome), a Cox proportional hazards model will be used with the following covariates:

1. Age (i.e., 50-80 years or >80 years).
2. Pre-fracture living setting (i.e., institutionalized or not institutionalized).
3. Pre-fracture functional status (i.e., using aid or independent ambulator).
4. American Society for Anesthesiologists (ASA) Class (i.e., Class I/II or III/IV/V).
5. Centre number.

Results will be reported as hazard ratios with 95% confidence intervals. Kaplan-Meier curves will be constructed.

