2.6 Outcome Definitions

Primary Outcome

| Outcome | Definition |
|---|---|
| Unplanned Secondary Hip Procedure (study event) | Unplanned secondary procedures that were classified as study events included: 
 ○ Closed reduction of hip dislocation ○ Open reduction of hip dislocation ○ Open reduction of fracture ○ Soft tissue procedure ○ Insertion of antibiotic spacer ○ Full implant exchange ○ Partial implant exchange – stem only ○ Partial implant exchange - head only ○ Partial implant exchange - liner only |

| Outcome | Definition |
|--|---|
| | 
 ○ Partial implant exchange - head and liner ○ Partial implant exchange – acetabular component only ○ Partial implant exchange – acetabular component and head ○ Implant adjustment – re-orientation of the stem ○ Implant adjustment – re-orientation of the acetabulum component ○ Implant removal with no replacement ○ Excision heterotopic ossification ○ Supplementary fixation ○ Other |
| Reason for Unplanned Secondary Procedure | 
Classification of the reason for unplanned secondary procedures included:
 
 ○ Treat a peri-prosthetic fracture ○ Treat hip instability or dislocation ○ Treat infection – superficial ○ Treat infection – deep ○ Treat wound necrosis ○ Treat another wound healing problem ○ Remove heterotopic ossification ○ Manage abductor failure ○ Manage another soft tissue problem (i.e. pseudotumor) ○ Correct implant failure –loosening or subsidence ○ Correct implant failure - breakage ○ Treat implant wear ○ Treat osteolysis ○ Treat implant corrosion ○ Improve function ○ Relieve pain |

Secondary Outcomes

| Outcome | Definition |
|--------------------------|---|
| Mortality | Mortality was adjudicated by the Central Adjudication Committee and it was considered to be an event if it occurred within 24-months of the initial hip fracture surgery. |
| Serious Adverse Events | Serious adverse events, as diagnosed by physicians at the clinical sites, were documented. A serious adverse event was defined as any adverse event that is fatal, life threatening, requires or prolongs hospital stay, results in persistent or significant disability or incapacity, a congenital anomaly or birth defect, or an important medical event, symptom, sign, illness, or experience that develops or worsens in severity during the study. |

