
2.7 Overview of Adjudication

Adjudication Processes

The following information was excerpted from the HEALTH Adjudication Charter, which documents the responsibilities of the Central Adjudication Committee and the adjudication processes for the HEALTH trial.

1) Fracture Eligibility

The Central Adjudication Committee adjudicated fracture eligibility for all patients based on available pre-surgery and post-surgery x-rays, and completed case report forms. If the fracture did not meet all inclusion criteria or met one of the exclusion criteria, the fracture was deemed ineligible.

2) Technical Placement of Prostheses

The Central Adjudication Committee adjudicated the technical placement of the prosthesis based on available pre-surgery and post-surgery x-rays to determine if the quality of the implant placement was acceptable or unacceptable. This was unrelated to fracture eligibility.

3) Additional Surgical Procedures

The Central Adjudication Committee adjudicated additional surgical procedures that occurred within two years of initial surgery after the participant had completed their 24-month visit (or following early withdrawal) to determine if they were study events. Planned surgeries were not considered study events. If a participant had multiple unplanned surgeries for one indication, each unplanned surgery was considered a study event in addition to the first. Any unplanned surgery after the initial fixation that satisfied the criteria below was considered to be a study event:

- Treat a peri-prosthetic fracture
- Treat hip instability or dislocation
- Treat infection – superficial
- Treat infection – deep
- Treat another wound healing problem
- Treat another soft tissue problem
- Remove heterotopic ossification
- Manage abductor failure
- Correct implant failure – loosening or subsidence
- Correct implant failure – breakage
- Treat implant wear and corrosion
- Treat osteolysis
- Treat neurovascular injury
- Improve function
- Relieve pain

The Central Adjudication Committee reviewed all available x-rays, and data from the patient's completed case report forms.

4) Hip-Related Complications

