2.8 Statistical Analyses for Primary and Secondary Outcomes

Analyses included patients in the groups to which they were assigned. Patients were censored at 24 months of follow-up or at the time of their last follow-up for patients lost to follow-up. The primary analysis was a proportional hazards model using a competing risk analysis (death as the competing risk) with time to the HEALTH primary study endpoint as the outcome. The independent variable was THA versus HA, and the following covariates were used: age (50-80 years or >80 years), pre-fracture living setting (institutionalized or not institutionalized), pre-fracture functional status (using aid or independent ambulator), and ASA Class (Class I/II or III/IV/V). For these covariates, we used values that were entered into the minimization system at time of enrollment. For our competing risk analyses, we used the method described by Zhou et al. to account for clustering within surgeons.⁶ The estimates from the competing risk analysis for clustered data analyses were marginal estimates. We report the treatment effects as hazard ratios (HRs) with 95% confidence intervals (CIs). No adjustment for multiplicity was made and the 95% CIs do not adjust for multiplicity. Kaplan-Meier curves were constructed for the primary outcome.

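### The SAP counts deaths from surgery rather than randomisation, so a death before the operation is literally not a mortality event, and the handling of unoperated patients is not stated

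*SAP*

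**What the plan says.** **Outcome windows start at surgery.** For mortality, SAP 2.6 says "it was considered to be an event if it occurred within 24-months of the initial hip fracture surgery". Protocol 3.2.1 defines the primary outcome as "any unplanned secondary procedure within 2 years of the initial joint replacement surgery", and under SAP 2.7 the adjudication committee "adjudicated additional surgical procedures that occurred within two years of initial surgery". Protocol 6.3 times every visit from surgery, and Protocol Appendix 1 makes surgery Day 0, after randomisation at enrolment.

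**The analysis is by allocation.** Protocol 7.2.1 states: "All outcome analyses will be performed by an intention to treat approach". SAP 2.8 likewise keeps patients in their assigned groups. It censors at 24 months of follow-up or at last contact, without saying when follow-up begins.

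**Surgeon is the cluster.** The primary competing-risk model uses a published method "to account for clustering within surgeons", and the mortality model in SAP 2.8 has a surgeon random effect. Neither says whether this is the allocated or the operating surgeon.

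**The interval from randomisation to surgery has no stated limit.** The inclusion criterion is "Operative treatment within 3 days (i.e. 72 hours) of the patient being medically cleared for surgery", so its clock starts at medical clearance. Surgical delay is recorded but not standardised (Protocol 5.2.5, SAP 2.4).

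**The concern.** Intention to treat compares everyone randomised from the moment of allocation. A death after allocation but before the operation belongs to that comparison. The mortality definition in SAP 2.6 leaves it out if followed to the letter, because such a death does not come after the surgery that opens the window. A patient who is never operated on has no date from which to count at all.

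The definitions can also disagree about one death. The serious adverse event definition in SAP 2.6 includes any fatal event and has no surgery-based window. A pre-surgery death could therefore be a fatal serious adverse event without being a mortality event.

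For the primary endpoint the matter is narrower. A secondary procedure needs a first operation, so no primary events are missed. What is unstated is whether unoperated patients are in the risk set, whether a pre-surgery death is coded as the competing event, and which surgeon identifies the cluster.

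The visible data-collection schedule does not obviously cover the interval. Protocol Figure 6 lists no adverse event form at the randomisation step, and in Appendix 1, as far as the table can be read, the early withdrawal form is first scheduled at 1 week.

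**Working it through.** **1. The plan's own figures, to see whether they are touched.** Protocol 7.1 gives 1,316 patients and 96 events, then 1,434 patients. Inputs: HA event risk 5% in year 1 and 1% in year 2, relative risk reduction 0.45 (hazard ratio about 0.55), mortality 15% and loss 5% per year, crossover 7.6%, two-sided alpha 0.05. Power for the primary outcome is not stated; 80% is assumed.

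- Events (Schoenfeld): 4 × (1.960 + 0.842)² / (ln 0.55)² = 87.8, so 88.
- Patients from the two-step yearly projection: 1,206 to 1,217. Divided by (1 − 0.076): 1,305 to 1,317 (stated 1,316).
- Projected events at 1,316 patients: 95.2 to 96.0 (stated 96).
- 1,316 × 1.09 = 1,434.4 (stated 1,434).

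The figures reproduce, and the time-origin question changes none of them.

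**2. Deaths between randomisation and surgery.** The documents give neither a count nor an interval. A 3-day wait is assumed, and so are the multipliers for a higher early hazard.

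- Daily hazard at 15% per year: −ln(0.85) / 365.25 = 0.000445.
- Expected deaths: 1,434 × [1 − exp(−0.000445 × m × 3)], where m multiplies the hazard.

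| m | Pre-surgery deaths | Share of 1,434 |
|---|---|---|
| 1 | 1.9 | 0.13% |
| 3 | 5.7 | 0.40% |
| 5 | 9.5 | 0.67% |
| 10 | 19.0 | 1.33% |

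**3. Against all deaths over two years.**

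- Ignoring loss to follow-up: 1,434 × (1 − 0.85²) = 398.
- With 5% annual loss as a competing exit, the yearly hazards are 0.1625 and 0.0513, together 0.2138. Deaths: 1,434 × (0.1625 / 0.2138) × [1 − exp(−2 × 0.2138)] = about 379.
- Relative to 398, the uncounted deaths are 1.9 / 398 = 0.5% up to 19.0 / 398 = 4.8%.
- Outer bound on imbalance: if every uncounted death fell in one arm (398 / 2 = 199 deaths), that arm's count would be short by 1.9 / 199 = 1% to 19.0 / 199 = about 10%. Nothing in the documents suggests such a split.

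**4. Patients never operated on.** If 1%, 2% or 5% (assumed) left the analysis and events fell in proportion, that is 14, 29 or 72 of 1,434 patients. The 96 events become 95.0, 94.1 or 91.2, and Schoenfeld power at hazard ratio 0.55 goes from 83.4% to 83.0%, 82.6% or 81.5%. Power is not the issue; the definition of the randomised comparison is.

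**The case against.** A reader might infer that patients who die or lose their operation while waiting are dropped from the trial's comparisons. The documents do not support that. No visible passage excludes them, SAP 2.8 analyses patients as assigned, and Protocol 6.5 and 7.2.1 commit to intention to treat. An outcome window is not an analysis set. The SAP text available starts at section 2.0, and the last item in its reference list, on post-randomisation exclusions, is not cited in that text, so a rule may stand in the missing part.

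A reader might also infer that clustering on surgeon makes it impossible to include an unoperated patient. It does not. The expertise-based design allocates patients to surgeons (Protocol 3.1 and 3.1.1), so the allocated surgeon could define the cluster, and SAP 2.10 plans the primary analysis without the surgeon term. What remains is that Protocol 6.1 describes allocation to one of two groups and no visible text says a named surgeon is recorded then. The SAP 2.10 analysis covers only the primary endpoint, so it does not help mortality.

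Nor does the protocol contradict itself on when follow-up starts. The phrase "available for continued follow-up between 12 and 24 months post-randomization" belongs to the sample-size projection; the visit schedule is anchored to surgery throughout.

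Finally, a reader might infer that waiting differs by arm because it depends on the allocated expert. Inclusion criterion 10 requires assurance that expertise in both procedures is available, and Protocol 5.2.1 lets qualified surgeons perform both. These limit the risk without setting an interval. A difference is possible but not shown.

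One point survives all of this: the mortality rule in SAP 2.6 is an explicit rule, and followed literally it does not count a death before surgery.

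**Conclusion.** The point holds for mortality as a matter of definition. SAP 2.6 starts the count at surgery, randomisation comes earlier, and intention to treat is promised for all outcomes. For the primary model it is a gap in the visible text about the risk set, the coding of pre-surgery deaths and the cluster of unoperated patients.

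The likely effect is small: about 2 deaths of 1,434 at the protocol's 15% annual mortality over an assumed 3-day wait, and about 6 to 19 if the early hazard is 3 to 10 times higher, against roughly 380 to 400 deaths. The wait and the multipliers are assumptions. To say that the rule breaks the randomised comparison of mortality would go beyond the documents, which show neither an exclusion nor an imbalance. It is still worth correcting, because the correction costs almost nothing and lets a reader verify the intention-to-treat claim.

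**What to change.** In SAP 2.6 and 2.8:

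- Run mortality from randomisation and count every death after randomisation, in all randomised patients, up to the same 24-month horizon.
- For the primary model, state the time origin, keep all randomised patients, and code a death before surgery as a competing event.
- For patients not operated on, use the allocated surgeon as the cluster, or a singleton cluster if no surgeon was recorded.
- The surgery-based window for secondary procedures may stay as a descriptive definition.
- Report by arm the interval from randomisation to surgery, the deaths before surgery, and the patients never operated on.

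If the part of the SAP before section 2.0 already has such a rule, refer to it in 2.6 and 2.8 and align the mortality definition with it. The SAP is written in the past tense, so if mortality was analysed from surgery, rerun it from randomisation.

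The cost is a few sentences and one small table. Randomisation is done through a central computerised system, so its dates should be at hand.

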
2.7 Overview of Adjudication

Adjudication Processes

The following information was excerpted from the HEALTH Adjudication Charter, which documents the responsibilities of the Central Adjudication Committee and the adjudication processes for the HEALTH trial.

1) Fracture Eligibility

The Central Adjudication Committee adjudicated fracture eligibility for all patients based on available pre-surgery and post-surgery x-rays, and completed case report forms. If the fracture did not meet all inclusion criteria or met one of the exclusion criteria, the fracture was deemed ineligible.

2) Technical Placement of Prostheses

The Central Adjudication Committee adjudicated the technical placement of the prosthesis based on available pre-surgery and post-surgery x-rays to determine if the quality of the implant placement was acceptable or unacceptable. This was unrelated to fracture eligibility.

3) Additional Surgical Procedures

The Central Adjudication Committee adjudicated additional surgical procedures that occurred within two years of initial surgery after the participant had completed their 24-month visit (or following early withdrawal) to determine if they were study events. Planned surgeries were not considered study events. If a participant had multiple unplanned surgeries for one indication, each unplanned surgery was considered a study event in addition to the first. Any unplanned surgery after the initial fixation that satisfied the criteria below was considered to be a study event:

- Treat a peri-prosthetic fracture
- Treat hip instability or dislocation
- Treat infection – superficial
- Treat infection – deep
- Treat another wound healing problem
- Treat another soft tissue problem
- Remove heterotopic ossification
- Manage abductor failure
- Correct implant failure – loosening or subsidence
- Correct implant failure – breakage
- Treat implant wear and corrosion
- Treat osteolysis
- Treat neurovascular injury
- Improve function
- Relieve pain

The Central Adjudication Committee reviewed all available x-rays, and data from the patient's completed case report forms.

4) Hip-Related Complications

The Central Adjudication Committee adjudicated adverse events related to the patient's randomized hip as reported by the clinical site after each participant had completed their 24-month follow-up (or following early withdrawal). The Central Adjudication Committee also reviewed all available x-rays (scheduled visits and unscheduled visits) to look for radiographic evidence of hip-related complications that were not reported by the clinical site. The Central Adjudication Committee was responsible for determining when the hip-related adverse event was first diagnosed/evident on participant x-rays. Hip-related complications that were considered study events included:

- f) Peri-prosthetic fracture
- g) Hip instability or dislocation
- h) Implant failure (loosening/subsidence and breakage)
- i) Wound healing problems (including superficial/deep infection, wound necrosis)
- j) Soft tissue problems (i.e. pseudotumor)
- k) Heterotopic ossification
- l) Abductor failure
- m) Implant wear and corrosion
- n) Osteolysis
- o) Neurovascular injury
- p) Decreased function
- q) Pain

The Chair of the Central Adjudication Committee independently reviewed all cases of heterotopic ossification that were identified by the Central Adjudication Committee. For each participant that was identified as having radiographic evidence of heterotopic ossification, the Chair independently reviewed the x-rays from each post-operative assessment and determined the severity of heterotopic ossification using the classification system developed by Brooker and colleagues:

- Stage I: Islands of bone within soft tissues of any size of the hip
- Stage II: Bone spurs from pelvis or femur, leaving at least 1 cm between opposing bone surfaces
- Stage III: Bone spurs from pelvis or femur reducing the space between opposing bone surfaces to less than 1 cm
- Stage IV: Ankylosis of the hip

The Central Adjudication Committee reviewed all available x-rays, and data from the patient's completed case report forms.

5) Mortality

The Central Adjudication Committee adjudicated mortality as required following a patient's early withdrawal. The Central Adjudication Committee reviewed all data from the patient's completed case report forms, available clinical notes, and/or x-rays to confirm the cause of death. They also commented on the relation to the treatment arm.

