## 6.3 Frequency and Duration of Follow-up

All patients will be followed for a period of 2 years (**Figures 6 and 7**). In addition, at the 2-year follow-up visit, the surgeon will document any secondary procedures that may be planned for the patient. Clinical assessments will occur at the time of admission to hospital (baseline), 1 week (24 hours – 10 days window), 10 weeks (8-12 weeks window), 6 months (5-7 months window), 12 months (11-13 months window), and 24 months ( $\geq 24$  months window) after surgery. X-rays will be taken at the time of admission to hospital (baseline), within 48 hours post surgery, and at 10 weeks (8-12 weeks window), 12 months (11-13 months window), and 24 months ( $\geq 24$  months window) post surgery. At 9 months (8-10 months window) and 18 months (17-19 months window) after surgery the research coordinator or nurse will ascertain patient status (i.e., secondary procedures, hip-related complications, deaths, as well as interview-administered quality of life questionnaires (SF-12, WOMAC, and EQ-5D)) via telephone calls and verifying information within medical records. At 1 week (24 hours – 10 days window), 10 weeks (8-12 weeks window), 6 months (5-7 months window), 12 months (11-13 months window), and 24 months ( $\geq 24$  months window) post surgery the research coordinator or nurse will ascertain patient status via clinical visits and completion of self-administered quality of life questionnaires (SF-12, WOMAC, and EQ-5D), and the functional mobility test (TUG).

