10 weeks (8-12 weeks window)	In Person/ Hospital/Clinic (if prior to D/C) or Telephone	•Follow-up Form, and TUG Test •SP, AE Forms •SF-12, WOMAC, EQ-5D (self-administered*) •Radiographs
	↓	
6 months (5-7 months window)	In Person/ Hospital/Clinic or Telephone	•Follow-up Form, and TUG Test •SP, AE Forms •SF-12, WOMAC, EQ-5D (self-administered*)
	↓	
9 months (8-10 months window)	Telephone or In Person/ Hospital/Clinic	•Follow-up Form •SP, AE Forms •SF-12, WOMAC, EQ-5D (interview-administered)
	↓	
12 months (11-13 months window)	In Person/ Hospital/Clinic or Telephone	•Follow-up Form, and TUG Test •SP, AE Forms •SF-12, WOMAC, EQ-5D (self-administered*) •Radiographs
	↓	
18 months (17-19 months window)	Telephone or In Person/ Hospital/Clinic	•Follow-up Form •SP, AE Forms •SF-12, WOMAC, EQ-5D (interview-administered)
	↓	
24 months (>24 months window)	In Person/ Hospital/Clinic or Telephone	•Follow-up Form, and TUG Test •SP, AE Forms •SF-12, WOMAC, EQ-5D (self-administered*) •Radiographs •Planned RS after 24 months

\* Prepare for interview-administered data collection if patient unable to complete self-administered forms.

AE = Adverse Event, D/C = Discharge, EQ-5D = EuroQol-5D, SP = Secondary Procedures, SF-12 = Short Form-12, TUG = Timed Up and Go, WOMAC = Western Ontario McMaster Osteoarthritis Index.

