2.5 Follow-up Processes

| Time-point | Assessment Procedures | Data Collection |
|-------------------------|---|---|
| 1 week (Up to 3 months) | In Person/Hospital/Clinic (if prior to discharge) | •Follow-up Form •Secondary Procedures, AE Forms •SF-12, WOMAC, EQ-5D (self-administered*) (asking about patient function prior to surgery) |

| | | |
|-----------------------------------|---|---|
| 1 week (Up to 5 weeks) | In Person/Hospital/Clinic (if prior to discharge) | •TUG Test |
| 10 weeks (5 weeks to 4 months) | In Person/Hospital/Clinic (if prior to discharge) or Telephone | •Follow-up Form and TUG Test •Secondary Procedures, AE Forms •SF-12, WOMAC, EQ-5D (self-administered*) •Radiographs |
| 6 months (4 to 7.5 months) | In Person/Hospital/Clinic or Telephone | •Follow-up Form and TUG Test •Secondary Procedures, AE Forms •SF-12, WOMAC, EQ-5D (self-administered*) |
| 9 months (7.5 to 10.5 months) | In Person/Hospital/Clinic or Telephone | •Follow-up Form •Secondary Procedures, AE Forms •SF-12, WOMAC, EQ-5D (interview-administered) |
| 12 months (10.5 to 15 months) | In Person/Hospital/Clinic or Telephone | •Follow-up Form and TUG Test •Secondary Procedures, AE Forms •SF-12, WOMAC, EQ-5D (self-administered*) •Radiographs |
| 18 months (15 to 21 months) | In Person/Hospital/Clinic or Telephone | •Follow-up Form •Secondary Procedures, AE Forms •SF-12, WOMAC, EQ-5D (interview-administered) |
| 24 months (21 to 30 months) | In Person/Hospital/Clinic or Telephone | •Follow-up Form and TUG Test •Secondary Procedures, AE Forms •SF-12, WOMAC, EQ-5D (self-administered*) •Radiographs •Planned revision surgery after 24 months |

* Interview-administered data collection done if patient was unable to complete self-administered forms.
 AE = Adverse Event, EQ-5D = EuroQol-5D, SF-12 = Short Form-12, TUG = Timed Up and Go, WOMAC = Western Ontario McMaster Osteoarthritis Index.

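### Read literally, the SAP's 24-month censoring excludes x-ray-only complications first seen on a closing film taken after month 24, so their risk is understated

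*SAP*

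**What the plan says.** - **Dating.** SAP 2.7, item 4, has the committee read all available films "to look for radiographic evidence of hip-related complications that were not reported by the clinical site". It adds: "The Central Adjudication Committee was responsible for determining when the hip-related adverse event was first diagnosed/evident on participant x-rays".
- **Censoring.** SAP 2.8, which covers primary and secondary outcomes, states: "Patients were censored at 24 months of follow-up or at the time of their last follow-up for patients lost to follow-up". It gives no separate rule for hip-related complications, and it does not define loss to follow-up.
- **Film schedule.** Protocol 6.3 states: "X-rays will be taken at the time of admission to hospital (baseline), within 48 hours post surgery, and at 10 weeks", then 12 and 24 months. No film is scheduled between those last two.
- **Closing window.** Protocol 6.3 and Appendix 1 put the closing visit at or after 24 months. Protocol Figure 7 has "24 months (>24 months window". SAP 2.5 has "24 months (21 to 30 months". The preceding film in SAP 2.5 is "12 months (10.5 to 15 months"; the Protocol gives 11 to 13 months.
- **Visit mode.** For the 12- and 24-month visits SAP 2.5 allows "In Person/Hospital/Clinic or Telephone", and Protocol Figure 7 also allows telephone, so a patient may finish without a closing film.
- **Event limits.** SAP 2.6 limits mortality to 24 months, and SAP 2.7 limits secondary procedures to two years. The hip-related complication definition has no such limit.
- **Modelling threshold.** SAP 2.8 fits proportional hazards models only for hip-related complications with at least 50 events, and reports 99% intervals.

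**The concern.** Each rule is reasonable alone, but together they conflict. Loosening, subsidence, osteolysis, wear or ossification that becomes visible after the 12-month film, with no symptoms that bring the patient to attention, is first evident on the closing film. If that film is taken at 25 months, the event is dated at month 25 and the patient has already been censored at month 24. Whether a second-year finding counts then depends on the date of the appointment.

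Two gaps sit beside this. A patient closed by telephone, with no film, appears to run to month 24 as free of film-detected complications. A patient whose closing visit was at 21 months also appears to run to month 24, unless classed as lost to follow-up.

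At stake are the reported risks of slow implant complications, the power to compare them, and whether some complications are modelled at all. SAP 2.11 counts the absence of a difference in hip-related complications among the grounds for its conclusions.

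**Working it through.** The documents give no event count, risk or power for hip-related complications, so there is no plan figure to reproduce. The check follows the stated rules through the visit windows.

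**1. Share of closing films after month 24.** Under the Protocol window, essentially all on-schedule films. Under the SAP window, if dates are uniform: (30 − 24)/(30 − 21) = 6/9 = 67%. A triangular distribution over 21 to 30 months that peaks at 24 also gives 67%.

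**2. Risk counted under the literal rule.** Assumptions: true 24-month risk 10%, constant hazard, everyone filmed, no deaths, 12-month film uniform over 10.5 to 15 months. The Protocol sets no upper limit for the closing film, so 24 to 30 months is assumed. Hazard per month: h = −ln(0.90)/24 = 0.00439. The risk detectable by a film at month t is 1 − exp(−h·t), averaged over the window.

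| Film | Window (months) | Detectable risk |
|---|---|---|
| 12-month | 10.5 to 15 | 5.44% |
| Closing, early part of SAP window | 21 to 24 | 9.40% |
| Closing, whole SAP window | 21 to 30 | 10.58% |
| Closing, Protocol window | 24 to 30 | 11.17% |

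- Protocol closing window: only findings up to the 12-month film count, 5.44%. Share kept = 5.44/11.17 = 49%.
- SAP closing window: (2/3 × 5.44%) + (1/3 × 9.40%) = 6.76%. Share kept = 6.76/10.58 = 64%.

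Simulation under the same assumptions gave 5.5% and 6.7%, with 49% and 64% kept. With the Protocol's own 11-to-13-month window for the 12-month film, the Protocol row falls to 5.1%, with 46% kept.

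**3. Power and the 50-event threshold.** Schoenfeld's formula, two-sided alpha 0.01, illustrative hazard ratio 1/(1 − 0.45) = 1.82 from the Protocol's sample-size effect: 100 events give 66% power, 63 events 42%, 50 events 32%. A complication with 60 events, of which 20% are first seen on late closing films, keeps 60 × 0.80 = 48 and is not modelled.

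**4. Treatment ratio.** With a constant hazard and equal film loss in both arms, the simulated risk ratio was 1.46 to 1.50 under the literal rule and 1.45 to 1.48 when all closing films count. With no true effect and closing films missing in 10% of one arm and 30% of the other, it was 0.96 to 1.04 under the literal rule and 0.90 to 1.12 when all closing films count. Missing films therefore need their own rule.

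**5. Film-free time under the literal rule.** Last film at 21 months: 24 − 21 = 3 months. Last film at the 12-month visit: 24 − 15 = 9 to 24 − 10.5 = 13.5 months.

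**6. Candidate fixes (SAP window, same assumptions).**
- Closing-film findings at month 24, film-negative patients also carried to month 24: estimated risk 10.6%, against a true 10%.
- Closing-film findings at month 24, film-negative patients censored at their film date: events at month 24 are 10.58% − 5.44% = 5.14% of patients. Film-negative patients still at risk are 2/3 × (1 − 0.1117) = 59.2%. Estimated risk = 1 − (1 − 0.0544) × [1 − 5.14/(5.14 + 59.2)] = 13.0%. This overstates the risk, because clean patients filmed before month 24 leave the risk set while positive ones stay.

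**The case against.** The strongest reply is that nothing in either document says these complications are excluded. Hip-related complications carry no 24-month limit, and 24 months of follow-up could mean the completed closing visit and not a day count. SAP 2.7 is excerpted from an adjudication charter that is not available here and might settle the point. This stands as a limit on certainty, hence the words 'read literally'. It does not remove the problem: if the censoring rule does not govern this outcome, SAP 2.8 has no event-date or censoring rule for it.

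The scope is also narrow. Dislocation, wound problems, neurovascular injury and pain are normally found clinically. Site-reported complications can carry their own diagnosis date. The 18-month contact asks about complications and checks records, unscheduled films are read too, and a telephone visit still collects clinical events. This stands: the exposure is confined to x-ray-only findings.

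A reader might infer four stronger things that the documents do not support:
- *Second-year films yield few or no events.* Under the SAP window a third of closing films (uniform dates) precede month 24 and count, and the 12-month film may be as late as month 15.
- *The second-year hazard ratio of 0.24 in SAP 2.11 shows the damage.* It concerns secondary procedures, which have their own two-year limit and do not depend on film detection.
- *The treatment comparison is biased.* Nothing in the documents shows that film timing, film completeness or complication timing differs by arm.
- *A patient closed at 21 months is certainly credited with three unseen months.* That rests on the SAP window alone and on an undefined term.

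**Conclusion.** The point holds as a conflict between stated rules. Taken literally, first-evident dating, 24-month censoring and a closing film that is mostly or wholly after month 24 leave out many x-ray-only complications that arise after the 12-month film. Under the assumptions above, about half (49%, Protocol window) to two thirds (64%, SAP window) of those ever detected are kept, and a true 10% risk reads as about 5.4% to 6.8%. The 10% risk, constant hazard, uniform dates, complete filming and absence of deaths are assumptions; the windows and rules come from the documents.

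The consequences are understated risk, lost power, and possibly a complication falling below the modelling threshold. Distortion of the hazard ratio is conditional on differences between arms and has not been demonstrated. The primary outcome is not affected by film dating.

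**What to change.** 1. Reconcile the 24-month window across Protocol 6.3, Figure 7 and Appendix 1 and SAP 2.5.
2. In SAP 2.8, for film-detected complications, assign a finding first evident on the 24-month-visit film to nominal month 24, and carry film-negative patients with a closing film to the same nominal month 24. Both halves are needed: month-24 event dating should not be paired with film-date censoring of clean patients (working, step 6). An interval-censored analysis could serve as a sensitivity check.
3. For film-only findings, censor patients with no closing film at the nominal time of their last film.
4. For clinical events, state that a patient whose last contact or record check is before 24 months is censored at that date.

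The cost is a few sentences in the SAP and re-derivation of event and censoring dates already held. The downside is that a few complications that began between 24 and 30 months are counted at month 24, in both arms; in the check this moves a true 10% to 10.6%.
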